4. Continuous eligibility assessments on Day -1 will be done only during Period 1, and continuous medical history on Day -1 and prior to dosing on Day 1 of each period.
5. Including sex, date of birth, race, and ethnicity.
6. Will be performed at Screening, at the admission of each period (Day -1), for each period: on Day 1 pre-dose (up to 60 minutes pre-dose), and 1 (± 20 min), 2 (± 20 min), 4 (± 20 min), 8 (± 60 min), 12 (± 60 min), and 16 (± 60 min) hours post-dose; on Day 2 (24 [± 60 min] hours post-dose); on Day 3 (48 [± 60 min] hours post-dose), and at Follow-up. Orthostatic vital signs will be measured at Screening and at admission on Day -1 only.
7. Will be started approximately 1-2 hours pre-dose at Day 1 of each period and will be continued to approximately 48 hours post-dose.
8. Will take place at Screening (in fasted state, i.e., participants should fast for 4 hours prior to sample collection), and in each period: on Day -1 (in fasted state), Day 1 at 8 hours post-dose (in not-fasted state), at Day 2 (in fasted state), at Day 3 (in fasted state), and at Follow-up (in fasted state). HbA1c will be performed at Screening.
9. Participants receiving Treatment A will be required to consume a high-calorie, high-fat meal 30 minutes prior to study drug administration. Participants receiving Treatment B will be administered the study drug under fasted state.
10. Will take place at pre-dose (within 2 hours of dosing) and at 0.25 (± 2 min), 0.5 (± 2 min), 1 (± 5 min), 1.5 (± 5 min), 2 (± 5 min), 3 (± 10 min), 4 (± 10 min), 6 (± 10 min), 8 (± 10 min), 12 (± 10 min), 16 (± 30 min), 24 (± 30 min), 36 (± 30 min), 48 (± 30 min), 72 (± 1 hr), and 96 (± 1 hr) hours post-dose.
11. In potential post-menopausal women only to confirm the post-menopausal status.
12. Women of childbearing potential (only) will have a urine pregnancy test at Screening and at discharge on Day 3, and a serum pregnancy test on Day -1 of each period.

Table 3: Schedule of Assessments (Part 2)

	Screening	Treatment						Outpatient Visits		Follow-Up ¹
	D-28 to -2	D-1	D1	D2	D3-11	D12	D13 (Discharge ² or early termination)	D15	D16	D19 (or between Day 19 and Day 22)
Informed consent	X									
Height and BMI	X									
Weight	X	X					X			
Inclusion/Exclusion Criteria	X	X ³	X ³							
Demographics ⁴	X									
Medical History		X ³								
Concomitant Medications							Continuously			
Physical and Neurological Examination	X	X					X			X

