11 STUDY ASSESSMENTS AND PROCEDURES

- Study procedures and their timing are summarized in the SoAs ([Table 1](#), [Table 2](#), and [Table 3](#)).
- All screening evaluations must be completed and reviewed to confirm that potential participants meet all eligibility criteria. The Investigator will maintain a screening log to record details of all participants screened and to confirm eligibility or record reasons for screening failure, as applicable.
- Procedures conducted as part of the participant's routine clinical management and obtained before signing of the Informed Consent Form (ICF) may be utilized for screening or baseline purposes provided the procedures met the protocol-specified criteria and were performed within the timeframe defined in the SoA.
- In the event of a significant study-continuity issue (eg, caused by a pandemic), alternate strategies for participant visits, assessments, medication distribution and monitoring may be implemented by the Sponsor or the Investigator, as per local health authority/ethics requirements.
- At time points when vitals, ECGs, and blood collections coincide, the order for conducting assessments should be ECGs first, then vital signs, and then blood sample collection. Sample collections done outside the pre-defined time windows will not be considered as protocol deviations since actual post-dose sampling times will be used for PK and statistical analyses. Actual collection times should be recorded on the eCRF.
- Blood and urine samples will be collected and processed as per the Analytical Methodology Information Sheet.

Repeat or unscheduled samples may be taken for safety reasons or for technical issues with the samples. The maximum amount of blood collected from each participant over the duration of the study, including that collected for eligibility and safety purposes and any extra assessments that may be required, will not exceed 250 mL for Part 1a and 350 mL for Parts 1b and Part 2.

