11.6.5 Clinical Safety Laboratory Tests

- See [Section 13.2](#) for the list of clinical laboratory tests to be performed and the SoA ([Section 4.1](#)) for the timing and frequency.
- The Investigator must review the laboratory results, document this review, and record any clinically significant changes occurring during the study as an AE. The laboratory results must be retained with source documents ([Section 10.1](#)).
- All laboratory tests with values considered clinically significantly abnormal during participation in the study should be repeated until the values return to normal or baseline or are no longer considered clinically significant by the Investigator or MM.
 - If clinically significant values do not return to normal/baseline within a period of time judged reasonable by the Investigator, the etiology should be identified, and the Sponsor notified.
 - All protocol-required laboratory tests, as defined in [Section 13.2](#), must be conducted in accordance with the site's standard procedures or SOPs.
 - If laboratory values from non-protocol-specified laboratory tests performed at the institution's local laboratory require a change in participant management or are considered clinically significant by the Investigator (eg, SAE or AE or dose modification), then the results must be recorded.

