- PK parameters related to time, such as time of maximum observed concentration (T_{max}) must be reported with the same precision as the actual sampling time, rounded to three decimal places.
- Concentration versus time data, as well as maximum observed concentration (C_{max}) shall be reported as they appear in the corresponding dataset.
- Ratios and 90% CIs, intra- and inter-participant coefficients of variation (CV), and CV (%) will be presented to two decimal places.

Only data from protocol scheduled (“nominal”) visits will be included in the summary tables. Data from unscheduled visits will not be included in the summary tables (unless they were used as baseline) but will be included in the listings.

This document is confidential.

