6.4 Missing Data

There will be no imputation for missing data, unless otherwise specified. Missing data shall be presented in participant listings as either “-” (unknown or not evaluated) or “N/A” (not applicable), with the corresponding definition in the footnotes. Missing descriptive statistics, or probability values (p-values), which cannot be estimated shall be presented as “-”.

For inclusion in concomitant medication and AE tables, incomplete start and stop dates on the eCRF will be imputed as follows:

- If the stop date is incomplete, the following rules will be applied:
 - Missing day: Assume the last day of the month
 - Missing day and month: Assume the last day of the year
 - Missing day, month, and year: Assume that the event/medication is continuing
 - In the case of the death of a participant, and if the imputed end date is after the date of death, the end date will be imputed as the date of death
- If the stop date is incomplete, imputed end date will be used instead of reported end date
- If the start date is incomplete, the following rules will be applied:
 - Missing day: Assume the first day of the month; however, if the partial date and the date of first study drug administration lie within the same month and year and the date of first study drug administration is not after the stop date of the event/medication, set to the date of study drug administration. Otherwise, set to the stop date of the event/medication.

This document is confidential.

- Missing day and month: Assume January 1st; however, if the partial date and the date of first study drug administration lie within the same year and the date of first study drug administration is not after the stop date of the event/medication, set to the date of first study drug administration. Otherwise, set them to stop date of the event/medication.
- Missing day, month, and year: Assume date of first study drug administration if it is not after the stop date for the event/medication. Otherwise, set them to stop date for the event/medication.

In the case of withdrawal of consent, all data from participants who withdraw from the study will be included in all summaries up to the time of withdrawal. For all other withdrawals, all data captured will be included in the safety summaries.

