10.5 Electrocardiograms (ECGs)

Electrocardiogram (ECG) values (ventricular heart rate and the PR, RR, QRS, QT, and corrected QT interval using Fridericia's formula [QTcF] intervals) will be listed by participant and summarized for each visit/timepoint by treatment. Observed values and changes from baseline will be presented.

A shift table representing the categorical change in overall interpretation (normal, abnormal not clinically significant, or abnormal clinically significant) from baseline to each post baseline timepoint will be presented.

Abnormal results will be flagged in the listings.

A frequency table with a QTcF interval reading change from triplicate baseline (average) to any single QTcF interval reading greater than 20 ms, 40 ms, or 60 ms will be presented. Participants will only be counted once in each category.

10.6 12-Lead Telemetry

12-lead telemetry will be conducted for evaluation of cardiac arrhythmias. Abnormal results will be listed by participant.

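### SAP 6.2 keeps unscheduled post-baseline values out of the summary tables, so an abnormality seen only off schedule reaches no value-based safety summary

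*SAP*

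**What the plan says.** SAP 6.2 restricts summary tables to data from scheduled visits and adds: "Data from unscheduled visits will not be included in the summary tables (unless they were used as baseline"). Such data still go into the listings.

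SAP 6.4 deals with withdrawn participants. After withdrawal of consent, "all data from participants who withdraw from the study will be included in all summaries up to the time of withdrawal". It then continues: "For all other withdrawals, all data captured will be included in the safety summaries". Neither section refers to the other.

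SAP 10.3 to 10.5 summarise laboratory values, vital signs and ECGs by visit or timepoint. Each also has a shift table from baseline to each post-baseline timepoint. The one table not built by timepoint is the QTcF frequency table, which counts a change from the averaged baseline to "any single QTcF interval reading greater than 20 ms, 40 ms, or 60 ms will be presented". It does not mention unscheduled readings.

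The protocol expects off-schedule readings. Section 11 states: "Repeat or unscheduled samples may be taken for safety reasons or for technical issues with the samples". Section 11.6.5 says that clinically significant laboratory values "should be repeated until the values return to normal or baseline" or are no longer judged significant. Section 11.6.3 calls for additional ECGs after a clinically significant ECG finding. In the schedules (4.1), the discharge column, Day 3 in Parts 1a and 1b and Day 13 in Part 2, also serves for a participant who leaves early ("or early termination").

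**The concern.** Changes from baseline in laboratory tests, ECGs and vital signs belong to the primary endpoint of every part (SAP 4.1.1, 4.2.1, 4.3.1). The values that 6.2 removes are not a random subset. Most arise because something was abnormal or a participant was unwell, so the exclusion is related to the outcome being summarised. In groups of six, one participant decides whether a cell reads zero. A shift table could then show only normal results at a dose where an abnormal result was recorded.

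The unclear rules add a practical risk. Two programmers following this SAP could produce different QTcF category tables, different tables for withdrawn participants and different Day 3 or Day 13 rows.

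**Working it through.** The plan gives no figure on this point, so the check sets the rules against the schedules.

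**1. Scheduled post-dose safety bloods** (Protocol Tables 1 and 3, footnotes on haematology and chemistry)
- Part 1a: Day 1 (8 h), Day 2, Day 3, follow-up on Day 8 to 11.
- Part 2: Day 1 (8 h), Days 2, 6 and 13, follow-up on Day 19 to 22. The gap from Day 6 to Day 13 is 13 − 6 = 7 days, all under daily dosing until Day 12.

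**2. One participant traced through the Part 2 tables.** Suppose an active participant has a normal baseline and normal values on Day 1, Day 2 and Day 6, a high value on an unscheduled sample between Day 7 and Day 12, and normal values on Day 13 and at follow-up.
- By-visit shift table (SAP 10.3): five rows, each normal to normal. Count of abnormal participants 0/6.
- By-visit descriptive statistics: the high value is absent under 6.2.
- Listing: present and flagged.
- TEAE tables (SAP 10.2): present only if the investigator judged the change clinically significant (Protocol 11.6.5, 13.3.1), and then as an event, not a value.
- A row using all post-dose values would read 1/6 = 16.7% for that dose, and 1/18 = 5.6% in the pooled active column (three cohorts of six, SAP Table 3.3-2).

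**3. Where the first abnormal value is scheduled.** If Day 6 itself is high, the Day 6 row shows it. The repeats that follow are left out, but many of them only document recovery. What can still be lost is a worse repeat: a higher peak, or a move from abnormal not clinically significant to abnormal clinically significant in the vital-sign and ECG shift tables.

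**4. Vital signs and ECG in Part 2.** These are scheduled pre-dose and at 4 h on each of Days 2 to 11, with more timepoints on Days 1 and 12. An abnormality seen only off schedule is less likely there than for laboratory tests.

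**5. Criteria that rely on repeats** (Protocol 7.3 and 10.1). QTcF prolongation is confirmed after 5 minutes; renal and haematological toxicity within 24 hours. A creatinine repeat after Day 6 in Part 2 falls by Day 7, which is off schedule. The dose-escalation list in 7.3 also includes a transaminase elevation lasting more than 2 weeks. In Part 1a the scheduled samples span at most 11 − 1 = 10 days (8 − 1 = 7 at the earliest follow-up), so a reading that completes this criterion must be off schedule.

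**6. The three unclear rules**
- *QTcF category table.* SAP 6.3 treats every measurement after dosing as post-baseline, which favours including all readings. SAP 6.2 is general and 10.5 states no exception to it. It is also unclear whether a 5-minute repeat at a scheduled timepoint counts as an unscheduled visit.
- *6.2 against 6.4.* One says which records enter tables; the other says whose data are kept. No sentence says which prevails for a withdrawn participant's unscheduled reading.
- *Early termination.* A participant who leaves Part 2 after, say, 4 of 12 doses has values in a column headed Day 13. The SAP has no rule for labelling them.

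**The case against.** The strongest reply is that little is truly hidden. AE incidence is part of the same primary endpoint, clinically significant findings must be recorded as AEs, and the TEAE tables are not organised by visit. Reasons for discontinuation are tabulated (SAP 7.1). Unscheduled values are listed with abnormal ones flagged. Dose escalation rests on the Safety Review Committee's review during the study, not on these final tables. The table shells are a separate document and may settle the visit labels. All of this stands, and it limits the point to value-based summaries. It does not remove it: a value out of range but not judged clinically significant has no TEAE route, and a TEAE row does not show the size of a change.

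Four stronger readings are tempting, and the documents do not support them:
- *The readings behind a stop vanish from the primary safety tables.* They should appear as TEAEs, and a first abnormal value at a scheduled timepoint stays in the value tables. Stopping treatment is also not withdrawal: Protocol 10.2 asks that such participants remain in the study for safety evaluation where possible.
- *SAP 6.2 and 6.4 contradict each other.* They can be read together, with 6.4 retaining the data and 6.2 governing display. What is missing is a statement of precedence.
- *The QTcF table excludes unscheduled readings, and early-termination values are shown as Day 13 or dropped.* The SAP states neither.
- *The safety bound shifts materially.* The exact one-sided 95% upper limits are 1 − 0.05^(1/6) = 39% for 0/6 and 58% for 1/6, the latter solving (1 − p)^6 + 6p(1 − p)^5 = 0.05. SAP 10 plans no inference on safety data, so the study will not report this comparison.

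**Conclusion.** The point holds in a limited form. SAP 6.2 is an explicit rule, and with shift tables that run only by timepoint it leaves an abnormality seen solely off schedule out of every value-based safety summary. The exposure is mainly in laboratory tests, most plainly in the 7-day gap in Part 2. The effect is one participant in six per dose for each such case; how often that will happen cannot be estimated from the documents. The conclusion assumes that the unseen table shells add no worst-value row and no exception to 6.2. The scope of the QTcF table, the precedence between 6.2 and 6.4, and the label for early termination are matters of clarity, not demonstrated errors. This is an inexpensive improvement to the reporting of a primary endpoint, not a threat to the conduct of the trial.

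**What to change.** - **SAP 6.2:** limit the scheduled-visit restriction to by-timepoint descriptive statistics and by-visit shift rows.
- **SAP 10.3 to 10.5:** add a worst-post-baseline row to the laboratory, vital-sign and ECG shift tables. State that this row and the QTcF category table use all post-dose values, including unscheduled, repeat and early-termination readings. For laboratory tests with low and high categories, say how a participant with both is counted.
- **Early termination:** tabulate it under its own label, not as Day 3 or Day 13.
- **SAP 6.4:** state that by-visit tables follow 6.2 for withdrawn participants as well.

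The cost is SAP wording, one extra row per shift table and the matching shell changes. No new data are needed. Abnormal counts may be slightly higher, and a worst-value row gives more weight to participants who were sampled more often, so it should be read beside the by-visit rows.

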6.3 Key Definitions

Baseline:

Unless stated otherwise, baseline is defined as the last value prior to the first dose. Post baseline will be considered as all measurements collected after study drug administration. “Unknown”, “Not Done”, “Not Applicable” and other classifications of missing data will not be considered when calculating baseline observations unless the finding is a valid categorical observation.

Study Day:

Study day will be calculated using first study drug administration date as the reference date. If the date of interest occurs on or after the first study drug administration date, study day will be calculated as (date of interest – first study drug administration date) + 1. If the date of interest occurs prior to the first study drug administration date, study day will be calculated as (date of interest – first study drug administration date). There will be no study Day 0.

Concomitant Medication:

Concomitant medication is defined as any medication taken by participants after dosing until the last study day.

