11.6.3 Electrocardiograms

12-Lead ECGs will be performed in triplicate, at least 1 minute apart, all within 10 minutes, and will be performed and interpreted according to the site's standard operating procedures. Average

values should be recorded. The ECGs will be performed after the participant has been resting in a supine position for at least 5 minutes. The ECG will electronically measure and calculate ventricular heart rate and the PR, RR, QRS, QT, and QTcF intervals. The QTcF interval will be used for clinical evaluations.

If a clinically significant abnormality is detected, the abnormality should be documented as an AE and followed until resolution with additional ECGs as medically indicated.

11.6.4 12-Lead Telemetry

12-Lead telemetry for evaluation of cardiac arrhythmias will be conducted at the time points noted in the SoAs.

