12.2 General Considerations

All collected data will be reported using summary tables and figures, as appropriate. Data summaries will be presented separately by part, dose, cohort, and overall. Tabulations will be produced for appropriate disposition, demographic, baseline, safety, and PK parameters. Categorical variables will be summarized by frequency distributions (number and percentages of participants) and continuous variables will be summarized by descriptive statistics (mean, standard deviation, median, minimum, and maximum). As appropriate, a 95% confidence interval (CI) will be presented. Graphical displays will be presented, as appropriate. All data will be provided in by-participant listings.

Baseline is defined as the last value prior to the first dose and will be flagged for all necessary analyses.

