6.1 General Methods

SAS for Windows software will be used to perform all statistical analyses. All relevant data in the database will be presented in the data listings. Unless otherwise stated, all listings will be sorted by study part, treatment, participant number, and assessment date/time. For the purposes of the summary tables, all participants randomized to placebo will be pooled into a single placebo group (i.e., All placebo). Unless otherwise stated, there will also be an overall section for all ATH-399A doses combined (i.e., All ATH-399A). All summaries will be presented separately for each study part. Unless otherwise stated, the descriptions of the analyses which follow apply to all study parts.

The following labels for treatment will be used on all tabulations where the results are displayed by treatment or sequence, in the following order:

Part 1a:

- All Placebo
- ATH-399A 5 mg
- ATH-399A 10 mg
- ATH-399A 20 mg
- ATH-399A 40 mg
- ATH-399A 80 mg
- All ATH-399A

Part 1b:

- Treatment A (Fed)
- Treatment B (Fasted)

or

This document is confidential.

- Sequence AB
- Sequence BA

Part 2:

- All Placebo
- ATH-399A TBD mg
- ATH-399A TBD mg
- ATH-399A TBD mg
- All ATH-399A

6.2 Summary Statistics:

Unless otherwise stated, continuous variables will be summarized using the number of observations (n), and the statistics mean, median, standard deviation (SD), minimum (min) and maximum (max). The min and max values will be presented to the same number of decimal places as recorded in the eCRF, mean and median will be presented to one more decimal place than the raw data, and the SD will be presented to two more decimal places than the raw data.

Summaries of change from baseline variables will include only participants who have both a baseline value and corresponding value at the timepoint of interest. Categorical and binary variables will be summarized with frequency counts and percentages. Percentages will be rounded to one decimal place, with the denominator being the number of participants (N) in the relevant population, unless otherwise stated.

All digits will be used for PK and statistical calculations. For PK tables and listings, the final reportable results or data will be presented by rounding off to two decimal digits, except for the following situations (this applies to individual data and descriptive statistics):

- Terminal elimination rate constant (λ_z) data shall be rounded off to four decimal places.

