8.6 Assessment of Food Effect

To assess the food effect on ATH-399A exposure in Part 1b, the values of AUC_{0-t} , $AUC_{0-\infty}$, and C_{max} calculated for the two diet regimens (fed and fasted) will be evaluated by ANOVA, with terms for sequence, period, and treatment as fixed effects and participant within sequence as a random effect. The exposure measurements ($AUCs$ and C_{max}) will be natural log-transformed prior to analysis. The model will be fitted using restricted maximum likelihood and the Kenward-Roger degrees of freedom approximation. [Error! Bookmark not defined.](#)

The 90% CI for the ratio of the geometric means for AUC_{0-t} , $AUC_{0-\infty}$, and C_{max} obtained between the fed and fasted conditions will be calculated. The absence of a food effect will be concluded when the 90% CI for the ratio of means (geometric means based on log transformed data) of fed and fasted conditions fall within 80% - 125% for AUC_{0-t} , $AUC_{0-\infty}$, and C_{max} .

The SAS code for the analysis model for ANOVA will follow the format given below (using the Mixed Procedure to fit the linear regression). The input variables, datasets, and labels are depicted in italicized red text and have been given generic names.

```
proc mixed data= dataset;
  class participant treatment sequence period;
  model var = treatment sequence period / solution ddfm= KR;
  random participant(sequence);
  lsmeans treatment / cl alpha= 0.1;
  estimate 'fed vs fasting' treatment 1 -1 / cl alpha= 0.1;
  ods output estimates = estimates covparms = covparms;
run;
```

Intra- and inter-participant CV% will also be estimated.

9. Pharmacodynamic (PD) Analyses

There will be no PD analyses for this study.

This document is confidential.

10. Safety

Safety and tolerability analysis will be performed for all participants in the safety population. No inferential statistical analysis of safety data is planned. For Parts 1a and 2, summary tables will be presented by dose (study drug and placebo) and by study drug overall. For Part 1b, summary tables will be presented by treatment and overall.

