10.3 Laboratory Evaluations

Laboratory data, including hematology, biochemistry, coagulation, urinalysis, and thyroid panel, will be listed by participant and summarized for each visit/timepoint by treatment. Observed values and changes from baseline will be presented.

In addition, a shift table representing the categorical change (low, normal, high) from baseline to each post baseline visit/timepoint will be presented.

Abnormal results will be flagged in the listings.

If more than one clinical laboratory is used, a formula that takes into consideration the relative normal ranges of each test of the laboratories will be utilized to normalize these data.^d The conversion formula used for each test will depend on the typical distribution of the normal range for the test.^e Prior to applying these formulas, units will be adjusted, as necessary. The laboratory which has the most results for each parameter will be considered primary in the formulas.

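### One first-dose baseline for all parts makes the Part 1b crossover's by-treatment safety tables mix same-period changes with Period 2 changes measured from before Period 1

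*SAP*

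**What the plan says.** - **Baseline.** SAP 6.3: "Unless stated otherwise, baseline is defined as the last value prior to the first dose". Protocol 12.2 has the same rule: "Baseline is defined as the last value prior to the first dose".
- **Post-baseline.** SAP 6.3: "Post baseline will be considered as all measurements collected after study drug administration".
- **Scope.** SAP 6.1: "Unless otherwise stated, the descriptions of the analyses which follow apply to all study parts".
- **Display.** The introduction to SAP 10 (Safety): "For Part 1b, summary tables will be presented by treatment and overall".
- **Tables that use baseline.** SAP 10.3 to 10.5 give changes from baseline and shift tables for laboratory tests, vital signs and ECG. For laboratory data, "a shift table representing the categorical change (low, normal, high) from baseline to each post baseline visit/timepoint will be presented". SAP 10.5 adds a count of participants by "change from triplicate baseline (average) to any single QTcF interval reading greater than 20 ms, 40 ms, or 60 ms". None of these sections names a period.
- **Departures.** SAP 11 reports none from the protocol.
- **Design and data.** Part 1b randomizes about 12 participants to AB or BA, with a washout of 7 days or more. Footnotes 6 and 8 of protocol Table 2 schedule vital signs and ECG on Day -1 and before dosing on Day 1, and laboratory tests on Day -1, in both periods.

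**The concern.** In Parts 1a and 2 there is one course of treatment, so a first-dose baseline is the natural reference. In a crossover tabulated by treatment it is not. Half of each fed or fasted column (the Period 1 half) is measured from just before dosing. The other half (Period 2) is measured from a value at least a week older, from before a different active dose. The Period 2 pre-dose readings are collected but not used as a reference.

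Read literally, the post-baseline rule also turns the Period 2 Day -1 and Day 1 pre-dose readings into post-baseline readings. Most summaries are by timepoint, so this matters mainly for the QTcF count, which takes any reading. The SAP does not say whether those readings enter it, or under which treatment.

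Change from baseline is a Part 1b primary endpoint (SAP 4.2.1). Part 1b has no placebo, so each treatment's own change is the main safety reference. At stake are the mean changes and their SDs, the shift cells and the mildest QTcF category.

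**Working it through.** The plan states no figure to reproduce here: safety is descriptive and the sample size is empirical. The check has three steps.

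**1. Between-period shift.** Let every Period 2 reading differ from Period 1 by d, with no drug effect. Fed is given in Period 2 to the BA participants, and fasted to the AB participants. With the first-dose baseline:

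- fed mean change moves by d × n(BA)/(n(AB)+n(BA))
- fasted mean change moves by d × n(AB)/(n(AB)+n(BA))

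With 6:6 (assumed), each moves by 6/12 = 0.5d and the difference is 0. With 6 AB and 5 BA, fed minus fasted moves by (5−6)/11 = −0.09d. With 6 and 4 it moves by (4−6)/10 = −0.20d. A same-period baseline removes d from both columns.

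**2. Spread of Day 1 QTcF change.** All SDs are assumptions: single reading s_r, within-day s_w and between-day s_d, with independent day effects. A triplicate mean varies around its day level with variance v = s_r²/3 + s_w².

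- Same-period baseline: variance of change = 2v.
- First-dose baseline in Period 2: 2v + 2s_d².
- Column of six Period 1 and six Period 2 changes: average variance = 2v + s_d².

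Example: s_r = 6, s_w = 0 and s_d = 4 give v = 12. The same-period SD is √24 = 4.90, the column SD is √40 = 6.32, and the ratio is 1.29.

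| Setting | s_r, s_w (ms) | Same-period SD | Column SD at s_d = 4, 6, 8 | Increase |
|---|---|---|---|---|
| A | 6, 0 | 4.90 | 6.32, 7.75, 9.38 | 29%, 58%, 91% |
| B | 6, 5 | 8.60 | 9.49, 10.49, 11.75 | 10%, 22%, 37% |
| C | 4, 5 | 7.79 | 8.76, 9.83, 11.17 | 12%, 26%, 43% |

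The range of about 10% to 90% covers these three settings. The remaining combination (s_r = 4, s_w = 0) has a same-period SD of only √(2×16/3) = 3.27 ms and gives 58% to 165%. The percentage is therefore sensitive to how small the same-period SD is assumed to be.

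**3. QTcF rise above 20 ms in Period 2, no drug effect.** Simulation of 400,000 participants per setting, with triplicates at 8 post-dose times (6 on Day 1, then 24 h and 48 h), single readings, post-dose readings only. Excess per column = 6 Period 2 participants × the difference in probability.

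| Setting | Same-period baseline (s_d = 4, 6, 8) | First-dose baseline | Extra participants per column |
|---|---|---|---|
| A | 8.5%, 14.9%, 22.0% | 14.6%, 24.2%, 32.9% | 0.36, 0.56, 0.66 |
| B | 27.5%, 31.6%, 36.0% | 30.8%, 36.4%, 41.6% | 0.20, 0.29, 0.34 |
| C | 14.3%, 18.9%, 24.4% | 18.5%, 26.1%, 33.0% | 0.25, 0.43, 0.52 |

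- With s_r = 4 and s_w = 0 the excess is 0.13 to 0.52.
- If Period 2 pre-dose readings also count, under the Period 2 treatment, the excess in A to C is 0.4 to 0.9.
- If only triplicate averages are available (protocol 11.6.3 asks for averages to be recorded), the post-dose excess in A to C is about 0.1 to 0.5.
- Above 40 ms the post-dose excess is at most 0.13 per column. Above 60 ms it is about 0.002 or less.
- In the overall column, where a participant counts once over both periods, the post-dose excess above 20 ms is +0.2 to +0.4 in A but −0.05 to −0.7 in B and C. Two period baselines give two chances of a low baseline; one shared baseline gives one.

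**The case against.** The strongest reply is that this is a choice between two defensible baselines. The study is first-in-human, and the washout may be adjusted on Part 1a data. A same-period baseline can absorb an effect that persists from Period 1, while a drug-naive one exposes it. That stands, and it is why the first-dose baseline should be kept as a secondary display rather than dropped. It does not justify having only that baseline in tables laid out by treatment.

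Second, the SAP rule opens with an allowance for exceptions, and the table shells are not among the documents. A period baseline may be specified there. If so, the governing definition in SAP 6.3 should say it.

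Third, the sizes rest on assumed SDs. This also stands. The direction per treatment column holds in every setting tried, but the size varies severalfold.

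A reader might infer more than the documents support:

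- **That the fed-versus-fasted safety contrast is biased.** With balanced, complete sequences the shared baseline cancels; only unequal sequences leave a fraction of d.
- **That overall QTcF outlier counts are inflated.** The sign there depends on the variance model, so no figure is claimed.
- **That only Day 1 vital signs and ECG gain day-to-day variation.** This is exact only if day effects are independent. Laboratory baselines are Day -1 samples in either period, and 24 h and 48 h readings fall on another day in any case. If nearby days are more alike than days a week apart, those changes are affected too.
- **That AE incidence or PK is affected.** Neither uses this baseline.

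**Conclusion.** The point holds and is worth considering, at modest weight. On the visible text, the Part 1b by-treatment changes, shift tables and QTcF categories mix two baseline lags, and Period 2 pre-dose readings formally become post-baseline.

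A between-period shift enters each treatment's mean change at half its size, given 6:6 sequences. The added variation falls mainly on Day 1 post-dose vital signs and ECG. The QTcF figures (SD up by about 10% to 90%, and 0.2 to 0.7 extra participants per column above 20 ms) illustrate settings A to C only and are not predictions for this trial. The higher categories barely change.

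Harm is limited because no safety inference is planned and observed values are tabulated beside the changes. Confidence is high for the wording of the rule, and lower for its size and for how the tables will be programmed.

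**What to change.** 1. In SAP 6.3, define the Part 1b baseline for vital signs, ECG and laboratory tests as the last non-missing value before dosing in the same period. Use it for the by-treatment change, shift and QTcF-category tables.
2. For these assessments, classify Period 2 Day -1 and Day 1 pre-dose values as Period 2 pre-dose, not post-baseline.
3. Keep the first-dose, drug-naive baseline for the follow-up visit and as a secondary display, so that any effect persisting from Period 1 stays visible.
4. Record the departure from protocol 12.2 in SAP 11.

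Parts 1a and 2 and the C-SSRS stay as they are. The change needs a few sentences and one period-level baseline flag. The readings are already scheduled in both periods. The downside is one extra set of Part 1b tables for about 12 participants.
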